#### 12.4.2 Analysis Plan

We will analyze the overall response rate of SCC based on the change in tumor area. Objective response rate (ORR) will be defined as the proportion of tumors with either a complete response or a partial response (PR) among all eligible and treated tumors. Toxicities will be graded according to the National Cancer Institute CTCAE v5.0. Exact binomial 90% confidence intervals (CIs) will be computed for the ORR. With a planned analysis on 30 per-protocol SCCs, this study would provide 91% power to reject an ORR of 15% if the true ORR is 40% or better, at one-sided alpha level of 0.05 with at least 9 responders.

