# **PROTOCOL SYNOPSIS**

TITLE	A Phase 2 Open-label, Single-arm Trial of the Efficacy and Safety of Topical Remetinostat Gel as Neoadjuvant Therapy in Patients with Squamous Cell Carcinoma Undergoing Surgical Resection				
STUDY PHASE	Phase 2				
INDICATION	Treatment of squamous cell carcinoma (SCC) and squamous cell carcinoma in situ (SCC-IS)				
INVESTIGATIONAL PRODUCT	Topical remetinostat gel 1%				
PRIMARY OBJECTIVE	To determine if topical remetinostat gel treatment 3-times-daily (TID) for 8 weeks will decrease SCC tumor area (in mm²) by at least 30%				
	To determine the overall response rate (ORR) of SCC tumors to 8 weeks of TID treatment with topical remetinostat gel				
SECONDARY OBJECTIVE	To assess the safety and tolerability of remetinostat gel 1% when applied topically TID under occlusion for 8 weeks as follows:				
	
 
Incidence, type, and severity of adverse events (AEs)
 
Incidence and nature of serious adverse events (SAEs)
 
				
	Incidence of AEs leading to remetinostat discontinuation or interruption				
	
 
Adherence to the treatment, measured by number of patients discontinuing the treatment (for any reason) and treatment interruptions
 
				
TREATMENT SUMMARY	Apply topical remetinostat gel 1% 3 times daily (TID) under bandage occlusion for 8 weeks				
STUDY POPULATION	Adults of either gender with squamous cell carcinoma (SCC) lesions ≥ 5 mm. See Section 3.1 for detailed eligibility.				
SAMPLE SIZE	30 SCC per-protocol evaluable tumors. The maximum number of subjects contributing evaluable tumors will be 40, but can be less to obtain the 30 SCC per-protocol evaluable tumors. Participating subjects that do not contribute evaluable tumors will not be counted towards this total. It is anticipated that no more than 40 subjects will participate overall.				

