# 2.4 Study Design

# For clinicaltrials.gov and Stanford Clinical Trials Directory compliance (see Section 10 for additional information)

- The primary purpose of this study is:
  - To determine if 8 weeks of topical remetinostat gel applied TID under occlusion will suppress SCC growth
  - To determine the overall response rate (ORR) of SCCs after 8 weeks of treatment with topical remetinostat gel 1%, as measured by at least 30% decrease in greatest area (in mm²).
- Subjects with at least 1 biopsy-proven cutaneous SCC will be recruited for this study.
- Subjects will apply remetinostat gel 1% to at least 1 SCC.
- Non-invasive cutaneous SCC lesions, including Bowen's disease, are also eligible for this study
- There is 1 treatment option: Topical remetinostat gel 1% applied 3 times daily.
- The study is a single-arm, open-label design
- For purposes of ClinicalTrials.gov, there is no secondary outcome.

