#### 3.3 Randomization Procedures

This study does not have randomization. All subjects must at least have one cutaneous SCC lesion and will apply topical remetinostat to SCC(s). If the subject has more than one SCC, a body map will remind subjects where to apply gel.

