#### 4. TREATMENT PLAN

Adult subjects in the clinic who have one or more biopsy-proven cutaneous SCC or SCC-in situ (hereafter referred to as "SCC") lesions greater than or equal to 5 mm in diameter, at least one of which is being biopsied as a normal course of care, will be invited to participate in this trial. Eligibility of prospective participants will be confirmed, and subjects will enroll according to stated inclusion and exclusion criteria.

Screening visits may be combined with or without day 1 visit.

Prospective participants must be willing to sign a consent form. Subjects will also give consent to donate their SCC tissue for biomarker measurement and apply medication 3-times daily under bandage occlusion for 8 weeks. The anticipated bandage will be an adhesive bandage (e.g., "Band-Aid") with a non-adherent dressing, or paper tape with a non-adherent dressing.

Drug treatment: Subjects will be instructed to apply topical remetinostat to individual SCCs 3-times daily (TID) for 8 weeks. Patients will be asked to discontinue application of the medication at 8 weeks, approximately 2 weeks prior to their surgical excision(s), as dermal irritation from study drug may interfere with lesion identification at excision.

At least 1 target SCC will be identified requiring surgical excision per standard of care. In addition to being measured and photographed, this lesion(s) may be biopsied. Week 8 biopsy may be collected at the time of surgical excision of lesion(s). Histopathological evaluation of the specimen may be performed.

After an initial treatment application demonstration by the study team, treatment applications will be self-administered by the subject or a caregiver. Patients will receive oral and written administration instructions at the outset of the trial as follows:

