The investigator has the right to discontinue a patient from study drug or withdraw a patient from the study at any time. In addition, patients have the right to voluntarily discontinue study drug or withdraw from the study at any time for any reason. Reasons for discontinuation of study drug or withdrawal from the study may include, but are not limited to, the following:

- Any subject who presents at screening or during treatment with a large (> 20 mm) SCC lesion: such a lesion will be discontinued from treatment (if applicable) and referred for evaluation for surgical resection. (If the patient has other, smaller lesions, these smaller lesions may be considered for enrollment in the study.)
- Subject withdrawal of consent at any time
- Any medical condition that the investigator or Sponsor determines may jeopardize the patient's safety if he or she continues in the study
- Investigator determines it is in the best interest of the patient
- Surgical or other treatment of target SCC before Week 8
- Pregnancy

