# 12.1 Statistical Design

The Primary Objective and Primary Outcome of this study is to determine if topical remetinostat will reduce SCC tumor size, as defined by at least 30% decrease in SCC tumor area (in mm²) at end of study as compared with baseline. Complete response (CR) will be defined as no clinically detectable tumor at EOS. ORR is defined as the proportion of tumors with either a complete response or a partial response (PR) among all eligible and treated lesions. Exact binomial 90% confidence intervals (CIs) will be computed for the ORR. With a planned analysis on 30 per-protocol SCCs, this study should provide 91% power to reject an ORR of 15% if the true ORR is 40% or better, at one-sided-alpha level of 0.05 with at least 9 responders.

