#### 12.4.1 Analysis Population

We will first analyze the data by intention to treat analysis and then per-protocol analysis by only including tumors ≥ 80% compliant with drug treatment. Tumors with 79% or less compliant with

drug treatment will be reported as a deviation; tumors at least 80% compliant with drug treatment will not be recorded as a deviation. Patients will be instructed to use a band-aid or other form of occlusion. If the patient has difficulty with band-aid usage, the patient may stop and this will be documented.

For subjects who drop out, we will use data from their last study visit if they contribute a biopsy. The analysis population will include participants who have consented to undergo remetinostat treatment and who have at least 1 SCC tumor.

Safety analyses will include all subjects who received at least one dose of study treatment. Graded AEs (number and percent) will be summarized and reported according to the NCI CTCAE v5.0.

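### The 9-of-30 rule, the exact 90% interval and the 91% power assume independent tumors, but subjects may contribute several and the analysis ignores within-subject correlation

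*Combined protocol and SAP*

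**What the plan says.** The unit of analysis is the tumor. Section 12.1 states: "ORR is defined as the proportion of tumors with either a complete response or a partial response (PR) among all eligible and treated lesions". Sections 12.1 and 12.4.2 attach an exact binomial 90% interval to that proportion: "Exact binomial 90% confidence intervals (CIs) will be computed for the ORR". They and section 12.6.2 give 91% power to reject 15% when the true ORR is 40%, at one-sided alpha 0.05, with 9 or more responders among 30 per-protocol tumors.

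Several tumors per subject are allowed:

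- Section 4 invites "Adult subjects in the clinic who have one or more biopsy-proven cutaneous SCC or SCC-in situ" lesions.
- Section 2.4: "Subjects will apply remetinostat gel 1% to at least 1 SCC".
- Section 3.3: "If the subject has more than one SCC, a body map will remind subjects where to apply gel".
- Section 4.2, for a subject with a lesion over 20 mm: "If the patient has other, smaller lesions, these smaller lesions may be considered for enrollment in the study". This is weaker support, because it concerns what may be enrolled in place of, or beside, the large lesion.

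The number of subjects is bounded only from above. The synopsis states: "The maximum number of subjects contributing evaluable tumors will be 40, but can be less to obtain the 30 SCC per-protocol evaluable tumors". Section 12.3 lists the number of tumors as a baseline descriptor, but nothing in section 12 uses it in the ORR analysis. Within-subject correlation, a clustered interval and a one-tumor-per-subject analysis are not mentioned.

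**The concern.** An exact binomial interval is exact only when the 30 outcomes are independent. Tumors on one subject share the person applying the gel, the application technique and the skin type, so positive correlation is plausible, although the documents do not quantify it. The 80% compliance rule narrows shared adherence in the per-protocol set only. Section 12.4.1 puts the other set first: "We will first analyze the data by intention to treat analysis and then per-protocol analysis".

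With positive correlation, 30 tumors carry less information than 30 independent observations. The 90% interval may then cover less than 90%, the rule may reject a 15% ORR more often than 5% of the time, and power may fall below 91%. The ORR and its interval are the planned primary evidence, and section 12.7 anticipates a randomized trial if the gel reduces SCC size. A cluster adjustment added later would have to be chosen with the data in view.

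**Working it through.** **Inputs from the plan.** n = 30 tumors; null 15%; alternative 40%; one-sided alpha 0.05; success at 9 or more responders; exact (Clopper-Pearson) 90% interval.

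**Step 1: reproduce the plan's figure.** For X ~ Binomial(30, p):

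- Power = P(X ≥ 9 | p = 0.40) = 90.6%, matching the stated 91%.
- Attained alpha = P(X ≥ 9 | p = 0.15) = 2.8%. A cutoff of 8 gives 7.0%, so 9 is the correct smallest cutoff.
- The lower 90% limit is 14.0% at 8/30 and 16.6% at 9/30. The rule is therefore the same as requiring the lower limit to exceed 15%.
- Coverage is 90.8% at ORR 40% and 92.4% at ORR 15%.

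The arithmetic is sound, given independence.

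**Step 2: allow correlation.** Assumptions: subject i has mᵢ tumors, with Σmᵢ = 30. Its responder count is beta-binomial with mean p and intraclass correlation ρ, so the beta parameters are p(1−ρ)/ρ and (1−p)(1−ρ)/ρ. The variance of the tumor-level ORR is inflated by 1 + ρ(Σmᵢ²/30 − 1). Examples at ρ = 0.3:

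- 15 subjects of two: 1 + 0.3 × (60/30 − 1) = 1.3; effective sample 30/1.3 = 23.1 tumors.
- 10 subjects of three: 1 + 0.3 × (90/30 − 1) = 1.6; effective sample 30/1.6 = 18.8 tumors.

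**Step 3: apply the unchanged rule and interval.** The distribution of the total is the exact convolution of the subject distributions. Layouts read subjects × tumors each; "skewed" is not a plan term and stands here for 15 subjects with one tumor, three with 3 and one with 6. Each cell gives ICC 0.1 / 0.3 / 0.5.

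| Layout | Alpha, % | Power, % | Coverage at ORR 40%, % |
|---|---|---|---|
| 30×1 | 2.8 at any ICC | 90.6 | 90.8 |
| 20×1 + 5×2 | 3.0 / 3.5 / 3.9 | 90 / 89 / 89 | 90.3 / 89.2 / 88.1 |
| 10×1 + 10×2 | 3.2 / 4.1 / 4.9 | 90 / 88 / 87 | 89.7 / 87.5 / 85.4 |
| 15×2 | 3.4 / 4.7 / 5.9 | 89 / 87 / 86 | 89.2 / 85.9 / 82.9 |
| 10×3 | 4.1 / 6.5 / 8.6 | 88 / 85 / 82 | 87.5 / 81.4 / 76.1 |
| Skewed | 3.9 / 6.1 / 8.1 | 89 / 86 / 83 | 88.2 / 83.0 / 78.2 |
| 6×5 (stress case) | 5.4 / 9.7 / 13.0 | 86 / 80 / 76 | 84.4 / 73.6 / 65.6 |

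**Step 4: where each limit is crossed.** ICC scanned in steps of 0.01.

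| Layout | Alpha > 5% | Coverage < 90% at ORR 40% | Coverage < 90% at ORR 15% |
|---|---|---|---|
| 20×1 + 5×2 | never up to 0.99 | 0.16 | 0.48 |
| 10×1 + 10×2 | 0.52 | 0.08 | 0.24 |
| 15×2 | 0.35 | 0.06 | 0.16 |
| Skewed | 0.20 | 0.04 | 0.11 |
| 10×3 | 0.17 | 0.03 | 0.09 |
| 6×5 | 0.09 | 0.02 | 0.05 |

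Power falls at every positive ICC. Coverage at ORR 40% is the first nominal limit to fail; alpha fails last, because it starts at 2.8%.

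**The case against.** The strongest reply is that the effect may be small or absent in practice.

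- Up to 40 subjects may supply 30 tumors, so one tumor each fits the text. Section 2.3 names transplant and other immunosuppressed patients among those most burdened by repeated surgery, and exclusion 9 in section 3.1 removes moderate to significant immunosuppression. Limits on lesion size and site remove further tumors. Heavily clustered layouts are therefore less likely.
- Alpha has a real cushion: 15 subjects of two tumors need an ICC of 0.35 to pass 5%. Coverage at ORR 15% also holds longer than at 40%.
- Mixed invasive and in-situ lesions at different sites could lower the ICC.
- The plan does prespecify one unambiguous analysis.
- Adjustment costs power even where the current test is valid. For 15×2 at ICC 0.3, alpha is already within 5%, yet adjusting takes power from 87% to about 79%.

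All of this stands as to likely size. It does not remove the gap. Section 2.3 also names extensive sun exposure as a cause of multiple lesions, and nothing in the plan limits the layout. A fixed analysis is no protection if its independence condition fails. The interval has much less cushion than the test.

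**Conclusion.** The concern holds, as an unstated condition and not as an arithmetic error. The 91% and the nominal 90% coverage are justified only if tumors respond independently, and the plan neither says so nor ensures it. With one tumor per subject there is no effect, and mild clustering is largely absorbed by the conservatism of the exact method. With two or three tumors per subject throughout and ICC 0.3, coverage at ORR 40% is 86% or 81%, power 87% or 85%, and alpha 4.7% or 6.5%. These figures rest on assumed layouts, assumed ICCs and a beta-binomial model. It should be fixed: it affects the primary endpoint, and the preferred repair needs no more subjects or procedures.

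**What to change.** Keep the tumor-level ORR as the point estimate and prespecify a subject-clustered 90% interval and test for both analysis sets. Other recognized cluster methods would also serve if fixed in advance. One ready form:

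> For subject i with mᵢ tumors and xᵢ responders, n tumors, k subjects, x = Σxᵢ and p = x/n, let V = [k/(k−1)] Σ(xᵢ − mᵢp)² / n² and d = max(1, V / [p(1−p)/n]). Set d = 1 if every subject has one tumor, or if all or no tumors respond. The 90% CI is the exact interval with x/d responders of n/d tumors, with limits Beta(0.05; x/d, n/d − x/d + 1) and Beta(0.95; x/d + 1, n/d − x/d). Success requires the lower limit to exceed 15%.

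With one tumor per subject and n = 30 this is the current 9/30 analysis. Add a caution that d is poorly estimated with few subjects. State the 91% as conditional on independent tumors, and report the adjusted test's power. By simulation (200,000 trials per cell):

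| Layout | Adjusted power at ICC 0 / 0.1 / 0.3 / 0.5, % |
|---|---|
| 20×1 + 5×2 | 90 / 90 / 88 / 86 |
| 10×1 + 10×2 | 89 / 88 / 85 / 82 |
| 15×2 | 88 / 85 / 79 / 74 |
| 10×3 | 89 / 85 / 75 / 65 |
| Skewed | 89 / 86 / 79 / 72 |
| 6×5 | 87 / 77 / 59 / 44 |

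Across these cells alpha is 2.0–3.2% and coverage at ORR 40% is 90–94%. Coverage at ORR 15% is 92–97%, except for 6×5 at ICC 0.5: 86.6%, against 64.9% unadjusted. There 11% of trials have no responder, so d = 1 and the upper limit of 9.5% misses 15%.

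**Cost.** SAP wording and a few lines of code, with no change in planned numbers. The price is power and width. For 15×2, power is about 87.5% against 90.6% at ICC 0, and 85% against 89.5% at ICC 0.1. Median interval width at ORR 40% is 32, 33 and 37 points at ICC 0, 0.1 and 0.3, against 32 for independent tumors.

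**Alternative.** Apply 9/30 to one target tumor per subject, designated before Day 1, with other tumors supportive. This keeps 91% power but needs 30 evaluable subjects. That is within the maximum of 40, but 5 more than the 25-subject layout and 20 more than the 10-subject layout above.

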#### 12.5 Secondary Analysis

#### 12.5.1 Analysis Population

Data from all enrolled patients will be included in the below safety evaluations.

#### 12.5.2 Analysis plan

For Secondary Objective 1, toxicities will be graded according to the National Cancer Institute CTCAE v5.0.

The safety of remetinostat when applied topically for 8 weeks will be assessed as follows:

- Incidence, type, and severity of adverse events (AEs)
- Incidence and nature of serious adverse events (SAEs)
- Incidence of AEs leading to treatment discontinuation or interruption
- Adherence to the treatment, measured by number of patients discontinuing the treatment (for any reason) and treatment interruptions

#### 12.6 Sample Size

#### 12.6.1 Overall Accrual estimates

Subjects will be enrolled from Stanford Dermatology (Adult) clinic which sees approximately 4,000 dermatology patients per month (or 48,000 visits per year). Approximately 20% of these patients have current or past skin cancer. Enrollment of SCC subjects for Stanford clinical trials has been rapid. 30 per-protocol SCC lesions are anticipated to be evaluated within the first 12 months. We will only advertise and enroll from Stanford Dermatology clinic. It is anticipated that at least 10 subjects will consent to baseline and post-treatment biopsies.

# 12.6.2 Sample size justification

For primary objective analysis, with a planned analysis on 30 per-protocol SCCs, this study would provide 91% power to reject an ORR of 15% if the true ORR is 40% or better, at one-sided alpha level of 0.05 with at least 9 responders.

## 12.6.3 Effect size justification

This is a single-arm (non-randomized) study of topical remetinostat. SCCs are not anticipated to self-regress in the absence of any treatment.

#### 12.7 Criteria for future studies

If topical remetinostat reduces SCC size, it is anticipated that a larger, randomized, controlled trial will be proposed.

# APPENDIX A: Study IRB-49542 Participant Medication Application Diary

# **Study Participant Study Drug Application Diary**

Participant l	ldentifier:	SCC-	

#### **STUDY DRUG INSTRUCTIONS:**

Study Drug: Remetinostat 1% gel

How Much: Apply a thin layer over the tumor(s) identified by the

study doctor.

How Often: Three times daily.

When: You should apply the gel in the morning, at mid-day, and in

the evening.

#### **SPECIAL INSTRUCTIONS:**

This medication must remain refrigerated at all times.

Cover the area with a bandage after you apply the gel.

Wash your hands after you apply the gel.

#### **APPLICATION LOG**

Please indicate if you applied the gel for each dose listed below.

Please bring this diary to your next clinic visit.

		Gel Applied			Comments
	Date	Dose 1	Dose 2	Dose 3	
Example	4/1/19	x	х	Х	Stinging after medication applied
Day 1	<pre><pre><pre>opulated date></pre></pre></pre>				
Day 2	<pre><pre><pre>opulated date></pre></pre></pre>				
Day 3	<pre><pre><pre>opulated date></pre></pre></pre>				
Day 4	<pre><pre><pre><pre>opulated date></pre></pre></pre></pre>				
Day 5	<pre><pre><pre><pre>opulated date></pre></pre></pre></pre>				
Day 6	<pre><pre><pre><pre>opulated date></pre></pre></pre></pre>				
Day 7	<pre><pre><pre><pre>opulated date></pre></pre></pre></pre>				
Day 8	<pre><pre><pre><pre>opulated date></pre></pre></pre></pre>				
Day 9	<pre><pre><pre><pre>opulated date></pre></pre></pre></pre>				
Day 10	<pre><pre><pre><pre>opulated date></pre></pre></pre></pre>				
Day 11	<pre><pre><pre><pre>opulated date></pre></pre></pre></pre>				
Day 12	<pre><pre><pre><pre>opulated date></pre></pre></pre></pre>				
Day 13	<pre><pre><pre><pre>opulated date></pre></pre></pre></pre>				

		Gel Applied			Comments
	Date	Dose 1	Dose 2	Dose 3	
Day 14	<pre><pre><pre><pre>opulated date></pre></pre></pre></pre>				
Day 15	<pre><pre><pre>opulated date></pre></pre></pre>				
Day 16	<pre><pre><pre>opulated date></pre></pre></pre>				
Day 17	<pre><pre><pre>opulated date></pre></pre></pre>				
Day 18	<pre><pre><pre><pre>opulated date></pre></pre></pre></pre>				
Day 19	<pre><pre><pre><pre>opulated date></pre></pre></pre></pre>				
Day 20	<pre><pre><pre><pre>opulated date></pre></pre></pre></pre>				
Day 21	<pre><pre><pre>opulated date></pre></pre></pre>				
Day 22	<pre><pre><pre><pre>opulated date></pre></pre></pre></pre>				
Day 23	<pre><pre><pre><pre>opulated date></pre></pre></pre></pre>				
Day 24	<pre><pre><pre>opulated date></pre></pre></pre>				
Day 25	<pre><pre><pre><pre>opulated date></pre></pre></pre></pre>				
Day 26	<pre><pre><pre><pre>opulated date></pre></pre></pre></pre>				
Day 27	<pre><pre><pre>opulated date></pre></pre></pre>				
Day 28	<pre><pre><pre><pre>opulated date></pre></pre></pre></pre>				
Day 29	<pre><pre><pre><pre>opulated date></pre></pre></pre></pre>				
Day 30	<pre><pre><pre><pre>opulated date></pre></pre></pre></pre>				
Day 31	<pre><pre><pre><pre>opulated date></pre></pre></pre></pre>				
Day 32	<pre><pre><pre><pre>opulated date></pre></pre></pre></pre>				
Day 33	<pre><pre><pre><pre>opulated date></pre></pre></pre></pre>				
Day 34	<pre><pre><pre><pre>opulated date></pre></pre></pre></pre>				
Day 35	<pre><pre><pre><pre>opulated date></pre></pre></pre></pre>				
Day 36	<pre><pre><pre><pre>opulated date></pre></pre></pre></pre>				
Day 37	<pre><pre><pre><pre>opulated date></pre></pre></pre></pre>				
Day 38	<pre><pre><pre><pre>opulated date></pre></pre></pre></pre>				
Day 39	<pre><pre><pre><pre>opulated date></pre></pre></pre></pre>				
Day 40	<pre><pre><pre><pre>opulated date></pre></pre></pre></pre>				
Day 41	<pre><pre><pre><pre>opulated date></pre></pre></pre></pre>				
Day 42	<pre><pre><pre><pre>opulated date></pre></pre></pre></pre>				
Day 43	<pre><pre><pre><pre>opulated date></pre></pre></pre></pre>				
Day 44	<pre><pre><pre><pre>opulated date></pre></pre></pre></pre>				
Day 45	<pre><pre><pre><pre>opulated date></pre></pre></pre></pre>				
Day 46	<pre><pre><pre><pre>opulated date></pre></pre></pre></pre>				
Day 47	<pre><pre><pre><pre>opulated date></pre></pre></pre></pre>				
Day 48	<pre><pre><pre><pre>opulated date></pre></pre></pre></pre>				
Day 49	<pre><pre><pre>opulated date></pre></pre></pre>				

